### **Handling of PK data below LLOQ or missing**

[figure not shown]
All concentration values below the lower limit of quantitation (LLOQ) are set to zero by the Bioanalyst, and will be displayed in the listings as zero and flagged. LLOQ values will be treated as zero in any calculations of summary statistics, and treated as missing for the calculation of the geometric means and their CV%. The number of non-zero concentrations will also be reported in the summary statistics.

Missing values for any PK data will not be imputed and will be treated as missing.

[figure not shown]
### **Population Pharmacokinetic Analysis**

[figure not shown]
All trametinib and dabrafenib concentration-time data may be combined and included in a population PK analysis that will examine the influence of demographics (especially age and weight) on the PK of study treatment. Trametinib and dabrafenib PK parameters estimated in the population PK analysis will include: apparent oral clearance (CL/F), central volume of distribution (Vc/F) and absorption rate constants (ka) (trametinib only). Data may be pooled with PK data from adult studies. These analyses will be documented in a separate analysis plan, and the results will be reported in a separate population PK report outside of the CSR.

[figure not shown]

## 2.11 Interim analysis

### Part A - Trametinib Dose-Escalation and Age Group Expansion

No interim analysis is planned for Part A, safety and PK data will be examined on an ongoing basis to support dose escalation decisions. Prior to determining the dose for the next cohort enrolled, [REDACTED]

[REDACTED] the  $C_{\tau}$  at steady state.

### Part B - Tumor-specific Expansion Cohort

An interim analysis is planned after all subjects have been enrolled in B3, NF-1 with PN cohort and have completed at least 3 post treatment assessments (Weeks 17, 33 and 49) or have discontinued treatment earlier. The results will be used for decision making for future development options and may be used for publications. At this time, no statistical hypothesis testing is planned, and no decision regarding the conduct of this study will be made.

At this interim analysis, all data collected at the time of the data cut-off for the interim analysis will be analyzed. In addition, safety and tolerability will be monitored closely on a continued basis.

### Part C – Combination Cohort

Prior to opening Part C the available safety and PK data from Parts A will be reviewed. Safety and PK data will be examined on an ongoing basis to support dose escalation decisions. Prior to determining the dose for the next cohort enrolled, [REDACTED]

### Part D – Expansion Cohort with Combination Therapy

An interim analysis is planned after all subjects have been enrolled in LGG cohort and have completed at least 12 months of treatment or have discontinued treatment earlier. The results will be used for decision making for future development options and may be used for publications. At this time, no statistical hypothesis testing is planned, and no decision regarding the conduct of this study will be made.

At this interim analysis, all data collected at the time of the data cut-off for the interim analysis will be analyzed. In addition, safety and tolerability will be monitored closely on a continued basis. A separate TOC will be added as an appendix for the interim analysis reporting effort.

## 3 Sample size calculation

### Part A - Trametinib Dose-Escalation and Age Group Expansion

The total number of patients to be enrolled in Part A will depend on the number of patients needed to characterize individual dose cohorts. The sample size is not driven by statistical considerations. However, it is anticipated that approximately 48 patients will be enrolled.

Given true incidence rates of DLTs, the associated probability of escalating to the next dose level in a 3+3 scheme are provided for reference below in [Table 3-1](#) 3-1.

**Table 3-1 Statistical Basis for Phase I Dose Escalation in a 3+3 Scheme**

True incidence of dose-limiting toxicity	10%	20%	30%	40%	50%	60%
Probability of escalating the dose	0.91	0.71	0.49	0.31	0.17	0.08

**Part B - Tumor-specific Expansion Cohort**

The sample size for Part B is based on feasibility, practicality, and what would be sufficient for the characterization of the safety of trametinib and the plasma PK for the populations enrolled. Each of the 4 expansion cohorts will enroll at least 10 evaluable patients, 5 patients in each cohort will be under the age of 6 years. Therefore, an estimated of at least 40 patients will be enrolled into Part B.

If less than 1 response is observed after x10 patients complete the study, the treatment could be considered to have insufficient clinical activity in that cohort. The estimated sample size (n=10) for the Part B expansion cohorts was further evaluated using exact binominal distribution probabilities ([Clopper CJ, et al.](#)), and the details are provided in [Table 3-2](#) and [Table 3-3](#).

For example, if zero responses are observed among 10 patients in a cohort [if the response rate (RR)=5%], the chance of declaring the cohort as having insufficient clinical activity after 10 patients is 60%. If the true RR=15% for trametinib in unresectable low grade gliomas patients, the chance approximately 20%. [Table 3-2](#) provides the corresponding 95% CIs around potential observed objective response rates given N=10 subjects. [Table 3-3](#) provides the corresponding 95% CIs around potential observed objective response rates given N=10 subjects.

**Table 3-2 Exact Binomial Probabilities of Observing 0 and 1 (or more) Responses in 10 Subjects**

True RR	Probability of Observing 0 responses in 10 Subjects	Probability of Observing $\geq 1$ Responses in 10 Subjects
5%	0.60	0.40
10%	0.35	0.65
15%	0.20	0.80
20%	0.11	0.89
25%	0.056	0.94
30%	0.028	0.97

**Table 3-3 Exact Binomial Probabilities of Observing 0 and 1 (or more) Responses in 10 Patients**

Observed Objective Response Rate	Exact 95% Confidence Interval (%) (N=10)
10%	0.3, 44.5
20%	2.5, 55.6
30%	6.7, 65.2
40%	12.2, 73.8
50%	18.7, 81.3
60%	26.2, 87.8
70%	34.8, 93.3

**Part C – Combination Cohort**

The total number of patients to be enrolled in Part C will depend on the number of patients needed to characterize individual dose cohorts. The sample size is not driven by statistical considerations. However, it is anticipated that approximately 18 patients will be enrolled.

**Part D – Expansion Cohort with Combination Therapy**

The sample size for Part D is based on feasibility, practicality, and what would be sufficient for the characterization of the safety and preliminary anti-tumor activity of trametinib/dabrafenib combination and the plasma PK for the populations enrolled. At least 20 subjects with LGG and at least 10 subjects with LCH will be enrolled. Therefore, it is estimated that at least 30 subjects will be enrolled into Part D.

The estimated sample size for the LGG and LCH cohorts in Part D is further evaluated using exact binominal distribution probabilities, and the details are provided in Table 3-4 and Table 3-5. For example, if the true RR=20% for trametinib and dabrafenib combination, the probability of observing < 6 responses out of 20 LGG subjects (observed response rate < 30%) is approximately 80%, and the probability of observing < 3 responses out of 10 LCH subjects (observed response rate < 30%) is approximately 68%. If the true RR=50%, the probability of observing at least 6 responses is > 97% given 20 LGG subjects, and the probability of observing at least 3 responses is > 94% given 10 LCH subjects. Table 3-6 provides the corresponding 95% CIs around potential observed objective response rates given N=20 subjects. The corresponding 95% CIs for potential observed response rates given N=10 is shown in 3.

**Table 3-4 Exact Binomial Probabilities of Observing less than 6 and at least 6 Responses in 20 Subjects**

True RR	Probability of Observing < 6 responses in 20 Subjects	Probability of Observing ≥ 6 Responses in 20 Subjects
20%	0.80	0.20
25%	0.62	0.38
30%	0.42	0.58
35%	0.25	0.75
40%	0.13	0.87
45%	0.06	0.94
50%	0.02	0.98
55%	0.01	0.99

**Table 3-5 Exact Binomial Probabilities of Observing less than 3 and at least 3 Responses in 10 Subjects**

True RR	Probability of Observing < 3 responses in 10 Subjects	Probability of Observing ≥ 3 Responses in 10 Subjects
20%	0.68	0.32
25%	0.53	0.47
30%	0.38	0.62
35%	0.26	0.74
40%	0.17	0.83
45%	0.10	0.90
50%	0.05	0.95
55%	0.03	0.97

**Table 3-6 Exact Binomial 95% Confidence Intervals around Potential Observed Objective Responses Rates for 20 Subjects**

Observed Objective Response Rate	Exact 95% Confidence Interval (%) (N=20)
20%	5.7, 43.7
30%	11.9, 54.3
40%	19.1, 63.9
50%	27.2, 72.8
60%	36.1, 80.9
70%	45.7, 88.1
80%	56.3, 94.3

## 4 Change to protocol specified analyses

No changes from the protocol specified analyses were made.

## 5 Appendix

### 5.1 Imputation rules

In general, imputed partial dates will not be used to derive study day, duration (e.g. duration of adverse events), or elapsed time variables.

Imputed dates will not be displayed in listings. However, where necessary, display macros may impute dates as temporary variables for the purpose of sorting data in listings only. In addition partial dates may be imputed for ‘slotting’ data to study time periods (see [\[Section 9.3 in Protocol\]](#)) or for specific analysis purposes as outlined below.

#### 5.1.1 Study drug

The following rule should be used for the imputation of the dose end date for a given study treatment component:

**Scenario 1:** If the dose end date is completely missing and there is no Study Treatment Discontinuation page and no death date, the patient is considered as on-going:

The patient should be treated as on-going and the cut-off date should be used as the last dosing date.

**Scenario 2:** If the dose end date is completely or partially missing and the Study Treatment Discontinuation page is available:

Case 1: The dose end date is completely missing, and the Study Treatment Discontinuation date is complete, then this latter date should be used.

Case 2: Only Year (yyyy) of the dose end date is available and yyyy < the year of Study Treatment Discontinuation date:

**Use Dec31yyyy**

Case 3: Only Year (yyyy) of the dose end date is available and yyyy = the year of Study Treatment Discontinuation date:

**Use Study Treatment Discontinuation date**

Case 4: Both Year (yyyy) and Month (mm) are available for dose end date, and yyyy = the year of Study Treatment Discontinuation date and mm < the month of Study Treatment Discontinuation date:

**Use last day of the Month (mm)**

All other cases should be considered as a data issue and the statistician should contact the data manager of the study.

After imputation, compare the imputed date with start date of treatment, if the imputed date is < start date of treatment:

**Use the treatment start date**

Patients with missing start dates are to be considered missing for all study treatment component related calculations and no imputation will be made. If start date is missing then end-date should not be imputed.

**5.1.2 AE, ConMeds and safety assessment date imputation**

**Table 5-1 Imputation of start dates (AE, CM) and assessments (LB, EG, VS)**

Missing Element	Rule
day, month, and year	
 
No imputation will be done for completely missing dates
 

day, month	
 
If available year = year of study treatment start date then                             
 
If stop date contains a full date and stop date is earlier than study treatment start date then set start date = 01JanYYYY
 
Else set start date = study treatment start date.
 
 
 
If available year > year of study treatment start date then 01JanYYYY
 
If available year < year of study treatment start date then 01JulYYYY
 

day	
 
If available month and year = month and year of study treatment start date then                             
 
If stop date contains a full date and stop date is earlier than study treatment start date then set start date= 01MONYYYY.
 
Else set start date = study treatment start date.
 
 
 
If available month and year > month and year of study treatment start date then 01MONYYYY
 
If available month and year < month year of study treatment start date then 15MONYYYY
 

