### **Baseline**

For safety and efficacy evaluations, the last available assessment on or before the date of start of study treatment is defined as “baseline” assessment. In case time of assessment and time of treatment start is captured (e.g. pre-dose ECG), the last available assessment before the treatment start date/time is used for baseline.

In rare cases where multiple measurements meet the baseline definition, with no further flag or label that can identify the chronological order, then the following rule should be applied: If values are from central and local laboratories, the value from central assessment should be considered as baseline. If multiple values are from the same laboratory (local or central) or collected for ECGs, then an average of all the pre-dose values should be considered as baseline.

Baseline blood pressure measurements are performed in triplicate and is the average of the second and third measurements.

For the laboratory evaluation of creatinine, the average (mean) of multiple assessments on or before study treatment start is defined as “baseline”.

If patients have no value as defined above, the baseline result will be missing.

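### Table 5-1 places partly dated lab, ECG and vital-sign results on the treatment start date, where an on-treatment result can become, or enter, the baseline

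*SAP*

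**What the plan says.** Four parts of the SAP act together.

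- **Section 5.1.2, Table 5-1.** Its title, "Imputation of start dates (AE, CM) and assessments (LB, EG, VS", puts laboratory (LB), ECG (EG) and vital-sign (VS) dates under the same rule as event and medication start dates. The rule has two triggers: day missing, "If available month and year = month and year of study treatment start date then"; day and month missing, "If available year = year of study treatment start date then". The exception begins "If stop date contains a full date and stop date is earlier than study treatment start date then set start date" and moves the date to the first of the month or year. The default is "Else set start date = study treatment start date".
- **Section 2.1.1, Baseline.** For safety and efficacy, "the last available assessment on or before the date of start of study treatment is defined as" baseline. If clock times of both assessment and first dose are recorded, the value must precede the dose. If several candidates cannot be put in order, a central laboratory value is preferred to a local one, and values from the same source are averaged. Creatinine baseline is the mean of all values up to treatment start.
- **Section 2.1.1, observation periods.** The on-treatment period opens on the date of first dose.
- **Section 5.1.** In general, "imputed partial dates will not be used to derive study day", durations or elapsed times. It allows imputation for assigning data to study periods and for the specific purposes set out in the subsections that follow.

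**The concern.** For an adverse event, defaulting to the treatment start date is conservative, because the event becomes treatment-emergent. For a measurement, the same date is also the last one on which a value can be baseline. A laboratory result taken two weeks into treatment, with its day unrecorded, can thus become the reference against which that patient's later results are judged. It also stops being a post-baseline value, because Section 2.1.1 computes change only for records after baseline.

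Laboratory values, ECG and vital signs are among the primary endpoints in Section 2.5.1. The outputs that depend on a correct baseline are:

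- the laboratory shift tables (Section 2.8.3);
- the liver criteria in multiples of baseline, including the Hy's Law definition (Section 2.8.3);
- newly occurring notable ECG values, which must be absent at baseline (Section 2.8.4.1);
- notable weight and blood-pressure changes (Table 2-9).

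**Working it through.** The SAP states no figure to reproduce. The check applies the rules as written and asks which true dates end up eligible for baseline.

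**1. Does the exception help?** It needs a complete stop date before treatment start. A single laboratory, ECG or vital-sign assessment normally has one date and no stop date, so it takes the default.

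**2. One worked date.** Assume treatment starts on 10 March 2016 and a blood sample taken on 24 March is recorded only as March 2016. Month and year match those of treatment start, so the sample is dated 10 March. That date satisfies the baseline definition and is later than any fully dated screening sample from before 10 March.

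**3. How many later days collapse onto the start date?** For the same start date:

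- Day missing: length of month − start day = 31 − 10 = **21 days**.
- Day and month missing: length of year − day of year = 366 − (31 + 29 + 10) = 366 − 70 = **296 days**.

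Over every possible start date in 2015, the count is 0 to 30 days (mean 14.7) with the day missing, and 0 to 364 days (mean 182) with day and month missing. These are counts of possible dates, not of patients.

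**4. Which partial dates are unaffected?** With the same start, April 2016 becomes 1 April 2016, February 2016 becomes 15 February 2016, and a bare 2017 becomes 1 January 2017. Each falls on the correct side of treatment start. Completely missing dates are not imputed.

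**5. Direction of the error.** Take the SAP criterion of ALT more than 3 times baseline, with ALT values of 30 and 200 assumed for illustration.

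| True baseline | Misplaced on-treatment value | Baseline used | Correct threshold | Threshold applied | Effect |
|---|---|---|---|---|---|
| 30 | 200 | 200 (replaced) | 3 × 30 = 90 | 3 × 200 = 600 | understated |
| 30 | 200 | (30 + 200)/2 = 115 (averaged) | 90 | 3 × 115 = 345 | understated |
| 200 | 30 | 30 (replaced) | 3 × 200 = 600 | 3 × 30 = 90 | overstated |

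In the first two rows the value of 200 exceeds the correct threshold but is no longer counted as post-baseline. In the third, a later value of 200, unchanged from the true baseline, would be counted as exceeding 3 times baseline.

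**6. Weight of one affected patient.** Section 2.8.3 summarises laboratory data by study part. With about 48 patients in Part A, one patient is 1/48 = 2.1 percentage points; with at least 40 in Part B, at most 1/40 = 2.5. Section 2.8 also asks for dose-level and disease-cohort summaries. In a group of 6, the size of the Part C extension, one patient is 1/6 = 17 points. That is the upper end, not a typical figure.

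**The case against.** **Imputed dates may be meant only for assigning data to periods.** No sentence says they feed baseline selection. For period assignment, the start date falls on-treatment, which is the conservative side. This is a fair reading of intent, but it does not close the gap. Section 5.1 also allows imputation for specific analysis purposes, the start date is both on-treatment and baseline-eligible, and no rule keeps the two uses apart.

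**The baseline definition has safeguards.** This stands in part. The clock-time rule may protect some ECGs, and the tie rule refers to flags or labels that establish order and to pre-dose values. However, the tie rule operates only when several values compete and cannot be ordered. An imputed result that is alone on the start date simply outranks earlier screening values. Where there is a tie, averaging dilutes the error without removing it.

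**The effect on worst values may be nil.** This also stands in part. Section 2.1.1 counts every scheduled, unscheduled and repeat value, so losing one matters to the worst post-baseline result only if no other is as bad. Grade 3 and 4 laboratory results are listed in any case. The wrong reference value remains.

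**Stronger readings that the SAP does not support.** A reader might infer that Table 5-1 contradicts Section 5.1. It does not: the restriction in 5.1 is general, covers study day, duration and elapsed time, and leaves room for the rules that follow. A reader might also infer that every such date biases results towards safety. It does not: a true pre-dose result in the start month remains a legitimate baseline candidate, and a misplaced result better than the true baseline overstates worsening.

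**Conclusion.** The point holds as a defect in a stated rule, not as a missing detail. As written, Table 5-1 and the baseline definition together allow an on-treatment laboratory, ECG or vital-sign result to replace the true baseline or be averaged into it. The error can run either way, and it understates worsening when the misplaced value is the worse of the two.

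The expected effect is probably small. Only partial dates in the start month, or year-only dates in the start year, are affected. The SAP does not say how many exist, and the analyses are descriptive, so no test or error rate is at stake. One affected patient moves a part-level percentage by about 2 to 2.5 points in Parts A and B, and by up to 17 points in a group of 6.

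The conclusion assumes that assessments carry no stop date and that the imputed date is used wherever the SAP does not forbid it.

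**What to change.** Add one sentence to Table 5-1 or to the baseline definition, covering laboratory, ECG and vital-sign results whose partial date has been set to the treatment start date:

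- The imputed date, if kept, is used only to assign the result to the on-treatment period.
- Such a result may not serve as baseline, or enter a baseline mean (creatinine included), unless its visit label identifies it as screening or pre-dose.
- An unscheduled result of this kind is never baseline and counts as post-baseline. Visit labels alone would leave these results without a rule.

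Results whose known month or year lies before treatment start need no change, since their order relative to first dose is not in doubt.

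The cost is one SAP sentence and a small programming change before database lock. A count of partial laboratory, ECG and vital-sign dates at that point would show whether any patient is affected.

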### **On-treatment assessment/event and observation periods**

For safety summaries, the overall observation periods will be divided into three mutually exclusive segments:

1. **Pre-treatment period:** from day of patient’s informed consent to the day before first administration of study treatment.

2. **On-treatment period:** from date of first administration of study treatment to 30 days after date of last actual administration of any study treatment (including start and stop date)
3. **Post-treatment period:** starting at day 31 after last administration of study treatment.

Safety summaries (tables, figures) include only data from the on-treatment period with the exception of baseline data which will also be summarized where appropriate (e.g. change from baseline summaries). In addition, a separate summary for death including on treatment and post treatment deaths will be provided. In particular, summary tables for adverse events (AEs) will summarize only on-treatment events, with a start date during the on-treatment period (*treatment-emergent* AEs).

However, all safety data (including those from the post-treatment period) will be listed and those collected during the pre-treatment and post-treatment period will be flagged.

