### **2.5.3 Handling of missing values/censoring/discontinuations**

As the duration of treatment for a given patient will depend on efficacy and tolerability, the duration of follow-up will vary between patients. Consequently there will be no imputation for missing data.

Patients will be treated until disease progression, until the patient is no longer obtaining clinical benefit from continued treatment, unacceptable toxicity, the study is terminated, or the patient withdraws consent or begins a new therapy. Patients who withdraw from the study will be included in summaries up to the time of withdrawal, regardless of the duration of treatment.

Patients with the designation of treatment relationship for adverse events (AEs) and serious adverse events (SAEs) missing will have the worst case assumed to impute the relationship: if relationship to study treatment is missing it will be assumed to be “Yes”. There will be no other imputation for missing data other than what’s described in Section 5.3 for partial dates and for missing exposure end dates.

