### **2.8.1 Adverse events (AEs)**

AEs will be graded according to the CTCAE, Version 4.0. Adverse events will be coded to the preferred term (PT) level using the Medical Dictionary for Regulatory Affairs (MedDRA dictionary). The latest available MedDRA version at the time of the analyses will be used. The MedDRA version used for reporting will be specified in the CSR and as a footnote in the applicable tables/listings.

AE summaries will include all AEs occurring during on treatment period. All AEs collected in the AE eCRF page will be listed along with information collected on those AEs (e.g. AE relationship to study drug, AE outcome, etc.) AEs with start date outside of on-treatment period will be flagged in the listings.

AEs will be summarized by number and percentage of patients having at least one AE, having at least one AE in each primary system organ class (SOC) and for each preferred term (PT) using MedDRA coding. A patient with multiple occurrences of an AE will be counted only once in the respective AE category. A patient with multiple CTCAE grades for the same preferred term will be summarized under the maximum CTCAE grade recorded for the event. AE with missing CTCAE grade will be included in the 'All grades' column of the summary tables.

In AE summaries, the primary system organ class will be presented alphabetically and the preferred terms will be sorted within primary SOC in descending frequency. The sort order for the preferred term will be based on their frequency.

The following adverse event summaries will be produced by dose for Part A and Part C dose exploration, by disease cohorts for Part B, by tumor-specific cohorts for Part D, by age group (< 2 years, 2 to < 6, 6 to 12, and 12 to 18 years) for monotherapy (Part A and Part B combined) and combination therapy (Part C and Part D combined) ;

- overview of adverse events
- Overview of deaths and SAEs,
- AEs by SOC, PT and severity (post-text)
- AEs by SOC and severity (in-text)
- AEs by PT and severity (in-text)
- AEs suspected to be related by SOC, PT and severity (post-text),
- AEs suspected to be related by PT and severity (in-text),
- SAEs by SOC, PT and severity (post-text)
- SAEs by PT and severity (in-text)
- AEs leading to study treatment discontinuation by SOC, PT and severity (post-text)
- AEs leading to study drug discontinuation by PT and severity (in-text),
- AEs leading to dose reductions, leading to dose interruptions, and leading to fatal outcome (post-text).

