**Table 5-2 Imputation of end dates (AE, CM)**

Missing Element	Rule (* = last treatment date plus 30 days ( not death date, cut-off date, withdrawal of consent date))
day, month, and year	
 
Completely missing end dates (incl. ongoing events) will be imputed by the end date of the on-treatment period*
 

Missing Element	Rule (* = last treatment date plus 30 days ( not death date, cut-off date, withdrawal of consent date))
day, month	

• If partial end date contains year only, set end date = earliest of 31DecYYYY or end date of the on-treatment period *

day	

• If partial end date contains month and year, set end date = earliest of last day of the month or end date of the on-treatment period*

Any AEs and ConMeds with partial/missing dates will be displayed as such in the data listings.

Any AEs and ConMeds which are continuing as per data cut-off will be shown as 'ongoing' rather than the end date provided.

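### An adverse event with no start date at all cannot enter the treatment-emergent AE tables, because the SAP admits events by start date and never imputes a wholly missing one

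*SAP*

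**What the plan says.** **Which events are tabulated.** SAP Section 2.1.1 (observation periods) says that "summary tables for adverse events (AEs) will summarize only on-treatment events, with a start date during the on-treatment period". The period runs "from date of first administration of study treatment to 30 days after date of last actual administration of any study treatment". Section 2.8.1 words the same restriction more loosely: "AE summaries will include all AEs occurring during on treatment period".

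**What happens to missing start dates.** Table 5-1 in Section 5.1.2 imputes partial start dates. If the known part matches the year, or the month and year, of treatment start, the event is placed at treatment start unless a full stop date is earlier. For a date with nothing recorded, the rule is "No imputation will be done for completely missing dates".

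**How other missing AE items are handled.**
- Causality, Section 2.5.3: "if relationship to study treatment is missing it will be assumed to be" Yes.
- Grade, Section 2.8.1: an AE without a CTCAE grade still counts in the all-grades column.
- End date, Table 5-2: "Completely missing end dates (incl. ongoing events) will be imputed by the end date of the on-treatment period".

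Section 2.5.3 otherwise rules out imputation, apart from partial dates and missing exposure end dates. All AEs are listed whether or not they are tabulated.

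**The concern.** AEs are a primary endpoint in all four parts (Section 2.5.1). The two rules are reasonable apart but together remove an event because of a data defect, not because it is known to lie outside treatment. This would apply equally to a serious event, to one that led to stopping treatment, or to one whose stop date falls well into treatment. The effect runs in one direction only, towards less reported toxicity. It also departs from how the same SAP treats missing causality, missing grade and partial start dates, each of which keeps the event in or leans towards the worse case.

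**Working it through.** The SAP gives no figure on this point to reproduce, so the check applies the rules and then sizes the effect of one omitted patient.

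**Step 1: apply Table 5-1, then the Section 2.1.1 window.** Assumed dates: first dose 10 March 2018, last dose 1 September 2018. The on-treatment period then ends 30 days later, on 1 October 2018. No stop date before the first dose is assumed.

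| Recorded start date | After Table 5-1 | In the window? |
|---|---|---|
| 2018 only | 10 Mar 2018 | yes, counted |
| Mar 2018 | 10 Mar 2018 | yes, counted |
| May 2018 | 1 May 2018 | yes, counted |
| 2017 only | 1 Jul 2017 | no, known to be earlier |
| nothing recorded | still missing | cannot be satisfied |

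Only the last row drops out without any evidence that the event began before treatment. Adding a stop date during treatment does not change that row, because Table 5-1 uses the stop date only when part of the start date is known.

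**Step 2: look for another route in.** None is stated.
- Section 2.5.3 allows no further imputation.
- The three periods in Section 2.1.1 are all defined by dates, so an undated event belongs to none of them.
- The listing flag in Section 2.8.1 is for start dates outside the period, so its value for an undated event is undefined.
- The rule for counting occurrences in the registry tables (Section 2.8.1) measures the gap from one event's end to the next event's start, so it also needs a start date.
- Under Table 5-2 the same event could receive an imputed end date at the close of the on-treatment period and still not be counted.

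**Step 3: size per affected patient.** Assume one patient whose only record of a given term has no start date. Cohort sizes are the planned minimums in Section 3: 10 for each Part B cohort and for LCH in Part D, and 20 for LGG in Part D. The change in incidence is 1/n:
- n = 10: 1/10 = 10 percentage points.
- n = 20: 1/20 = 5 percentage points.

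Exact (Clopper-Pearson) 95% limits, as in the SAP's own tables, use an upper limit of 1 − 0.025^(1/n) for 0/n and a lower limit of 1 − 0.975^(1/n) for 1/n. The upper limit for 1/n is the 0.975 quantile of Beta(2, n − 1).

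| n | As written | If the event is counted |
|---|---|---|
| 10 | 0/10: 0 to 30.8% | 1/10: 0.3 to 44.5% |
| 20 | 0/20: 0 to 16.8% | 1/20: 0.1 to 24.9% |

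The interval for 1/10 agrees with the 10% row of SAP Table 3-3.

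**The case against.** **The exclusion is inferred.** No sentence in the SAP says that undated AEs are not treatment-emergent, and the looser wording in Section 2.8.1 could be read to admit them. This stands as a caution. But Section 2.1.1 is the more specific rule, and a programmer who follows it has no basis for including the event. That the two wordings differ is a further reason to align them.

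**Not imputing is consistent policy.** Section 2.5.3 sets a general rule against imputation, and a wholly missing date offers nothing to anchor one. Table 5-1 also covers laboratory, ECG, vital-sign and medication dates, where declining to invent a date is sensible. This is fair as far as it goes. The remedy does not require a date to be invented, only a rule for classifying the event.

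**The effect may be nil.** Nothing in the SAP suggests that such events exist, and data cleaning may remove them. The figures of 10 and 5 points use minimum cohort sizes. They apply only if the patient has no other dated record of the term, and they shrink in the pooled monotherapy and combination tables. All of this stands and limits the size of the point. A prespecified rule is still needed for whatever cleaning leaves unresolved.

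**Two stronger readings that the SAP does not support.**
- A reader might infer that an undated AE vanishes from all safety output. It does not. The all-deaths summary (Section 2.8.2), the laboratory tables (2.8.3), ECG and LVEF (2.8.4), vital signs (2.8.5) and the reasons for discontinuing treatment (2.3.1) do not depend on AE start dates, and the event remains in the listings.
- A reader might also infer that an AE present before dosing that worsens on treatment is lost. Such an event has a known start date, so Table 5-1 is not the cause. Whether it is counted depends on whether a rise in grade is entered as a new record, which this SAP does not state. Section 2.8.1 says "A patient with multiple CTCAE grades for the same preferred term will be summarized under the maximum CTCAE grade recorded for the event", which fits either convention. Its rule for joining consecutive AEs of the same term regardless of severity suggests that changes in severity may be separate dated records.

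**Conclusion.** The point holds for AEs and SAEs whose start date is completely missing. Applied as written, Section 2.1.1 and Table 5-1 give them no way into the treatment-emergent AE, SAE, related-AE, AE-leading-to-discontinuation and AESI tables. The bias can only be downward. Its size per affected patient is about 10 points at n = 10 and 5 points at n = 20, assuming no other dated record of the term. The total effect cannot be computed, because the number of undated events is not given and may be zero. This is a cheap correction to the rule for a primary endpoint. It is not evidence that the safety results are materially wrong, and nothing is concluded here about AEs that worsen after starting before treatment.

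**What to change.** State in Section 2.1.1 and in the first row of Table 5-1 that an AE with a completely missing start date is counted as treatment-emergent unless its stop date is before the first dose of study treatment. The date itself can stay missing in listings. Align the inclusion wording of Sections 2.1.1 and 2.8.1 so that both express one rule.

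The cost is a sentence or two of SAP text and a change to the treatment-emergent flag, made before database lock. The downside is that a few events of unknown date that in fact began before treatment may be counted, making AE rates slightly less favourable. That is the same direction the SAP already accepts for missing causality.
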